## 6.2 Schedule of Assessments

For the complete schedule of assessments, refer to Appendix I of the clinical study protocol.

## 6.3 Treatments

### 6.3.1 *Treatments Administered*

Within 7 days after registration, the subjects will initiate treatment. The subjects will be given up to 12 percutaneous LOAd703 i.t. injections combined with atezolizumab, both administered every 3 weeks. Two cohorts consisting of at least 3 subjects per cohort will be evaluated. The LOAd703 dose will be escalated, one dose per cohort, to evaluate the following dose levels:  $1 \times 10^{11}$  virus particles (VP) per injection (cohort 1) and  $5 \times 10^{11}$  VP per injection (cohort 2). The treatment will be administered by percutaneous i.t. injection which may be image-guided depending on the tumor location.

Atezolizumab will be administered IV using a fixed dose (1200 mg/infusion).

On the day of the treatment, [REDACTED]

[REDACTED] LOAd703 dose, dose modifications and omissions will be carried out as per instructions in Sections 5.6.8 and 7.2.5 of the protocol.

Atezolizumab dose, dose modifications, and omissions will be instituted per standard guidelines and Section 7.2.5 of the protocol.

Missed LOAd703 or atezolizumab doses will not be made up in order to maintain adherence to the protocol schedule.

For the first 2 LOAd703 treatments of any trial subject, the subjects are monitored overnight. Vital signs will be noted [REDACTED]

### ***6.3.2 Method of Assigning Subjects to Treatment Groups***

Subjects will be assigned to the active dose cohort at the time of their enrollment into the study.

## **6.4 Safety and Efficacy Variables**

The following safety and efficacy endpoints are defined for this study:

Primary:

- Safety, determined by the National Cancer Institute Common Toxicity Criteria for Adverse Events (NCI CTCAE) v5.0.

Secondary:

- Overall response rate (ORR) evaluated by RECIST v1.1.

- Sheding determined as level of LOAd703 in [REDACTED]

- LOAd703 leakage to blood [REDACTED]

- Anti-adenovirus immunity [REDACTED]

- [REDACTED]

- [REDACTED]

- Immune profile as [REDACTED]

- [REDACTED]

Other:

- Changes in clinical laboratory evaluations, vital signs, Eastern Cooperative Oncology Group (ECOG) performance status scores, physical examination results, and 12-lead electrocardiogram (ECG).
- Clinical benefit rate (CBR) evaluated by RECIST v1.1.
- CBR including mixed response (MR).
- Time to progression (TTP) and progression free survival (PFS) evaluated by RECIST v1.1.
- Overall survival (OS).
- Metabolic response [including metabolic overall response rate (MORR) and metabolic clinical benefit rate (MCBR)] assessed using European Organisation for Research and Treatment of Cancer (EORTC) criteria in a subset of subjects where positron emission tomography (PET) scans were performed.

#### ***6.4.1 Description of Safety Variables***

##### ***6.4.1.1 Dose Limiting Toxicities***

As LOAd703 will be dose escalated, the subjects will be monitored for dose limiting toxicity (DLT). DLT is defined as any grade 3 or higher toxicity according to the NCI CTCAE version 5.0 that is attributed (definitely, possibly, or probably) to LOAd703. A DLT attributed to LOAd703 will lead to dose reduction.

[REDACTED] Subjects 2 and 3 should start treatment at least 24 hours apart.

All 3 subjects in the cohort must have been evaluated for DLT before decision on dose escalation is taken for the next cohort.

Toxicity attributed to atezolizumab will not be assessed as DLTs in the study but can still lead to dose modifications.

If a subject experiences an AE grade 3 or higher that can be attributed to the LOAd703 injection procedure (i.e., a bacterial infection, injection site pain, etc.), to disease, or another unrelated cause, it is not a DLT. Serious AEs (SAEs) due to injection procedure can lead to a change of injection procedure (such as change of lesion) instead of treatment discontinuation, depending on the type of AE and the risk of recurrence of the AE.

[REDACTED]

[REDACTED]

#### 6.4.1.2 *Adverse Events*

An AE is any untoward medical occurrence that does not necessarily have to have a causal relationship with the treatment. An AE can therefore be any unfavorable, unintended clinical sign, symptom, disease or clinically relevant change in laboratory variables or clinical tests temporally associated with the use of an investigational product, whether or not considered related to the investigation product, that requires clinical intervention or further investigation (beyond ordering a repeat/confirmatory test). Injury or accidents, medical conditions for operations that are not preplanned, or deterioration of the concurrent illness are also considered as AEs.

AEs are graded in the study according to NCI CTCAE version 5.0. All AEs (except for grade 1 and 2 laboratory abnormalities that do not require an intervention) are to be recorded on the AE page in the electronic case report form (eCRF).

During [REDACTED], the Investigator will note the occurrence and nature of each subject's existing medical condition(s). Occurrence and nature of AEs (including laboratory events) directly observed by the study personnel or spontaneously reported by the subject during the study will be reported. Each subject will be asked about AEs at each visit after the first dose of the investigational products LOAd703 and/or atezolizumab.

The general AE reporting period for this trial begins upon receiving the first LOAd703 and/or atezolizumab treatment and continues until final clinical follow-up visit at [REDACTED].

If both study treatments are prematurely withdrawn, AEs should be recorded [REDACTED]

If subjects are prematurely withdrawn from the study and enter survival follow-up (i.e., survival follow-up subjects), they will be followed for a minimum [REDACTED]

If a subject experiences an AE after signing the informed consent, but before treatment is started, the event will be recorded as an existing medical condition unless the Investigator believes that the event may have causal relationship to a study-specific procedure described in the protocol. If LOAd703 and/or atezolizumab have been administrated when an AE occurs, its relationship to the study drugs will be judged by the Investigator.

#### 6.4.1.3 Clinical Laboratory Parameters

Blood sampling should be done at [REDACTED]

If treatments are discontinued, sampling should still be collected at all scheduled visits up to [REDACTED]

The following parameters will be analyzed:

**Serum chemistry:** [REDACTED]

[REDACTED]

[REDACTED]

**Hematology:** [REDACTED]

[REDACTED]

[REDACTED]

[REDACTED]

In addition, [REDACTED]

Blood samples are collected prior to the initiation of pre-medications or treatments according to local hospital routines and sent to the local laboratory for analyses.

**6.4.1.4      *Vital Signs***

At [REDACTED] blood pressure and pulse will be recorded.

Following LOAd703 treatments: [REDACTED]

Following atezolizumab treatments: [REDACTED]

**6.4.1.5      *ECOG Performance Status***

ECOG performance status grade will be recorded at [REDACTED]

If treatments are discontinued, ECOG score will still be evaluated at all scheduled visits up to [REDACTED]

**6.4.1.6      *12-Lead Electrocardiogram***

A 12-lead electrocardiogram (ECG) will be performed after 5 minutes rest at [REDACTED] and the results will be judged clinically normal or abnormal by the Investigator. Any abnormality will be explained in the eCRF.

**6.4.1.7      *Physical Examination***

A physical examination will be performed at [REDACTED]. The physical assessment includes, but is not limited to, assessment of head/neck, chest/lungs, skin, abdomen, lymph nodes and the cardiovascular system. Other assessments should be added as applicable. The outcome

will be recorded as “normal” or “abnormal”. Abnormal findings will be assessed as “clinically significant” or “not clinically significant”.

#### ***6.4.2 Description of Efficacy Variables***

The tumor response will be evaluated using an appropriate imaging technique, depending on the localization of the tumor. Tumor regression or progression will be evaluated according to RECIST v1.1 criteria ([Eisenhauer 2009](#)). Further details are contained with the study protocol.

Due to the potential immunostimulatory capacity of the study treatments, it is possible that the induced immune stimulation may induce an inflammatory swelling of the tumor that initially may be mistaken for progression. Therefore, progressive disease (PD) during study participation leading to discontinuation of repeated treatment needs to be confirmed by radiological imaging at a later time point (within 4-12 weeks) and/or by a biopsy and/or tumor serum marker to confirm tumor progression.

Separate from the RECIST assessment, at each visit, subjects will also be assessed (by the Investigator) for MR, defined as one or more lesions fulfilling the criteria for PR and other(s) for PD.

In addition to computed tomography (CT)/magnetic resonance imaging (MRI) imaging, PET may be performed as a part of the tumor assessment (at the discretion of the Investigator). If PET is used, the measures are documented according to the EORTC assessment ([Aide 2019](#)):

- Complete metabolic response (CMR)
- Partial metabolic response (PMR)
- Stable metabolic disease (SMD)
- Progressive metabolic disease (PMD)
- Not evaluable (NE)

Metabolic response is defined as a  $\geq 15\%$  decrease in maximum standardized uptake value (SUVmax) and metabolic progression as a  $\geq 25\%$  increase in SUVmax.

##### ***6.4.2.1 Primary Efficacy Variable***

There is no primary efficacy endpoint in this study.

[figure not shown]
##### ***6.4.2.2 Secondary Efficacy Variable***

The secondary efficacy endpoint is:

- ORR defined as the proportion of subjects with a best overall response (BOR) of CR or PR (according to RECIST v1.1).

BOR is defined as the best response achieved by a subject over the whole study.

An additional BOR variable will also be derived which includes a category of MR. If a subject has PD according to RECIST v1.1 but the investigator has assessed the subject as having mixed response, then the response at that visit will be classified as MR. In this additional BOR derivation, MR is classed as a better response than PD.

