#### **4.4.2 Survival follow-up patient**

If another treatment is initiated due to progressive disease or other reasons, the patient will be followed for survival until death or End of Study (see section 7.5.3 *Survival Follow-Up*). The final clinical follow-up visit ( [REDACTED] ) should then be scheduled to collect endpoint data ( [REDACTED] ) as close to the start of new treatment as possible.

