#### **Partial Response (PR)**

A reduction of at least 30% in the sum of all tumor diameters from baseline.

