#### **Stable Disease (SD)**

Neither PR nor progressive disease.

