#### **Progressive Disease (PD)**

At least a 20% increase in the sum of all tumor diameters from the smallest tumor size and/or the appearance of new tumor lesion(s).

**Confirmation of Progression:** Due to the potential immunostimulatory capacity of the study treatments, it is possible that the induced immune stimulation may induce an inflammatory swelling of the tumor that initially may be mistaken for progression. Therefore, PD during study participation leading to discontinuation of repeated treatment needs to be confirmed by radiological imaging at a later time point (within 4-12 weeks) and/or by a biopsy and/or tumor serum marker to confirm tumor progression.

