#### 6.4.2.3 Other Efficacy Variables

Other efficacy endpoints are:

- CBR according to RECIST v1.1, defined as the proportion of subjects with a BOR of CR, PR, or stable disease (SD).
- CBR according to the BOR definition which includes MR, defined as the proportion of subjects with a BOR of MR or better (i.e., CR, PR, SD, or MR).
- Time to progression defined as the time from first dose of study treatment until progression according to RECIST v1.1. Subjects without progression are censored at the date of the last evaluable tumor assessment. If a subject does not have any evaluable post-dose tumor assessments, they will be censored at the date of first dose plus 1 day.
- Progression free survival defined as the time from first dose of study treatment until progression according to RECIST v1.1 or death (whichever occurs first). Subjects without progression/death are right censored at the date of the last evaluable tumor assessment. If a subject does not have any evaluable post-dose tumor assessments, they will be censored at the date of first dose plus 1 day.
- Overall survival defined as the time from first dose of study treatment until death. Subjects without death are right censored at the date of last contact.

[REDACTED]

[REDACTED]

[REDACTED]

[REDACTED]

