### 7.1.2 *Summarization by Visit*

Data summarized by study visit will be based on the nominal, scheduled visit label as reported on the eCRF.

Data collected at unscheduled visits will not be included in by-visit summaries but will be considered when endpoint derivations potentially include multiple visits (e.g.,

determination of baseline value, determination of worst post-baseline value, etc.). All data will be included in subject listings.

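### As written, one qualifying scan makes a responder: best overall response has no visible confirmation step for CR or PR, so a confirmed ORR should be reported beside the single-scan ORR

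*SAP*

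**What the plan says.** SAP 6.4.2.2 names one secondary efficacy endpoint: "ORR defined as the proportion of subjects with a best overall response (BOR) of CR or PR (according to RECIST v1.1". The next sentence gives the derivation: "BOR is defined as the best response achieved by a subject over the whole study". No blacked-out text is visible in that section.

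Protocol 8.1 defines PR as "A reduction of at least 30% in the sum of all tumor diameters from baseline", with no second scan, and SD as "Neither PR nor progressive disease", with no minimum time. Its CR definition likewise asks for one observation. SAP 6.4.2.3 adds "CBR according to RECIST v1.1, defined as the proportion of subjects with a BOR of CR, PR, or stable disease (SD".

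Protocol 7.5.1 schedules radiology every 9 weeks, plus or minus one week, and Protocol 3.4 limits clinic visits to 60 weeks. The synopsis plans at least 25 response-evaluable patients at the MTD. SAP 6.4.2.1 states that there is no primary efficacy endpoint, and SAP 7.6.5.1 calls all results descriptive.

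**The concern.** Taking the best of several noisy readings pushes error one way. A patient whose tumour sum has truly shrunk by less than 30% gets a fresh chance to cross the line at every scan, and a later reading back above the line does not undo the PR. There is no control arm in which the same error would occur, and the visible text describes no central or blinded reading. With about 25 patients at the MTD, each extra responder is worth 1/25 = 4 percentage points. Because the analysis is descriptive, readers will rely on the point estimate and its interval, and the interval does not correct this kind of error.

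**Working it through.** The visible text gives no target ORR, null rate or expected ORR, so there is no efficacy figure to reproduce. The check covers the number of chances, the effect of the rule under assumed reading error, and what that means for 25 patients.

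**1. Number of chances.** Scans every 9 weeks within 60 weeks fall at weeks 9, 18, 27, 36, 45 and 54, which makes six. With the one-week window, two successive scans are at least 9 - 2 = 7 weeks apart, so the planned schedule already meets a 4-week confirmation interval.

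**2. Direction.** Every confirmed responder is also a single-scan responder. Hence single-scan ORR is at least as high as confirmed ORR, and the two are equal only if every response is confirmed.

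**3. Size, under assumptions.** The baseline sum and each later sum carry independent log-normal error with SD s. The true change t is stable. PR is called when scan/baseline is 0.70 or less. For one scan,

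P(PR) = Φ( [ln 0.70 - ln(1+t)] / (s√2) ).

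- t = -20%, s = 0.10: ln(0.70/0.80) = -0.1335; -0.1335/0.1414 = -0.944; P = 0.17.
- t = -35%, s = 0.10: ln(0.70/0.65) = 0.0741; 0.0741/0.1414 = 0.524; P = 0.70.

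Over several scans the baseline error is shared, so the multi-scan results come from simulation (400,000 patients, 4 scans):

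| True change | s | PR at least once | PR on two consecutive scans |
|---|---|---|---|
| -10% | 0.08 / 0.10 / 0.12 | 4% / 11% / 19% | 0.5% / 2% / 4% |
| -20% | 0.08 / 0.10 / 0.12 | 30% / 40% / 47% | 8% / 13% / 18% |
| -35% | 0.08 / 0.10 / 0.12 | 95% / 93% / 91% | 78% / 73% / 70% |

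With s = 0.10 and a true -20%, the pair is 28% against 7% for 2 scans and 47% against 18% for 6 scans.

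**4. In 25 patients (s = 0.10, 4 scans).** Suppose 5 patients have a true -20%, 5 have a true -35%, and the other 15 never come near the threshold. The true ORR is then 5/25 = 20%.

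- Single scan: 5 × 0.399 + 5 × 0.928 = 2.0 + 4.6 = 6.6 responders, or 26.5%.
- Confirmed: 5 × 0.134 + 5 × 0.732 = 0.7 + 3.7 = 4.3 responders, or 17.3%.

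In this example the single-scan figure is too high and the confirmed figure too low.

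**5. A second route.** If 10% to 40% of single-scan responders fail confirmation (again an assumption), 8/25 = 32% falls to between 8 × 0.9/25 = 28.8% and 8 × 0.6/25 = 19.2%. Across starting counts of 5 to 10 responders the drop is 2 to 16 points. The exact 95% interval for 8/25 is 14.9% to 53.5%.

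**The case against.** **Silence is not a rule, and text is missing.** Both documents point to RECIST v1.1 for response. Text is blacked out after the ORR definition in Protocol 8.1, in Protocol 7.5 and after the endpoints in SAP 6.4.2.3. SAP 7.6.3 opens in mid-description, so part of it is not visible. A separate sponsor instruction on effect evaluation is cited but not supplied. A confirmation rule could sit in any of these. This stands as a limit: the claim is about the visible text. It does not remove the point, because SAP 6.4.2.2 states a working derivation of its own with no cross-reference.

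**Confirmation loses true responders.** This stands, as the -35% row shows, and it argues against simply replacing one rate by the other.

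**The stakes are limited.** This also stands. Safety is the primary endpoint, no visible decision depends on ORR, and a shift of one to three patients lies within sampling error.

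Three stronger readings are tempting, but the documents do not support them:

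- *CBR is inflated too.* An unconfirmed PR would normally become SD, which still counts in CBR, so missing CR/PR confirmation does not raise it.
- *PD must be confirmed but response need not be, so BOR is lopsided.* Protocol 8.1 says that PD leading to discontinuation "needs to be confirmed by radiological imaging at a later time point (within 4-12 weeks" or by other stated means. That rule governs stopping treatment. The visible BOR, TTP and PFS definitions contain no such step. The reason given, inflammatory swelling, enlarges tumours and is no evidence of false shrinkage.
- *A patient who leaves at week 4 or 5 counts as SD and so as clinical benefit.* SAP 7.1.2 says that unscheduled data "will be considered when endpoint derivations potentially include multiple visits", and Protocol 4.4.2 places the final visit "as close to the start of new treatment as possible". But the content of that visit, the Efficacy Evaluable Population and the minimum treatment for response evaluation are all blacked out. Scheduled scans already give SD a floor of about 8 weeks.

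**Conclusion.** The point holds for ORR. On the visible text a single scan is enough for CR or PR, and ORR under that rule is never below a confirmed ORR. The direction relative to a confirmed rate is certain. The size is not: it rests on assumed reading error of 8% to 12%, independent errors, stable true change and 4 scans. On those assumptions a stable -20% is called PR in 30% to 47% of patients on the single-scan rule and in 8% to 18% on the confirmed rule. A reader might infer that the trial's ORR will be overstated. The documents support only that it can be, since the mix of patients near the threshold is unknown and the single-scan rule also misses a few true responders. A minimum duration for SD is a minor, conditional safeguard. It matters only if off-schedule early scans occur in patients who count as efficacy evaluable.

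**What to change.** In SAP 6.4.2.2, keep the present definition, label it single-scan, and add a confirmed BOR and ORR: CR or PR criteria met again at the next assessment, at least 4 weeks later. State how an unconfirmed CR or PR is classed in the confirmed BOR; classing it as SD leaves CBR unchanged. In SAP 7.6.3, report both rates side by side, each labelled. If a confirmation rule already exists in text not visible here, cite it in 6.4.2.2. Optionally, require SD to be documented at least 8 weeks after first dose, which is the early edge of the first scan window; this changes nothing for scans done on schedule.

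The cost is some SAP wording, one derived variable and one extra row. No visit or scan is added. The confirmed rate will be equal or lower, will miss some borderline true responders, and will leave a response first seen on the last scan unconfirmed. That is why both rows should be shown.

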## **5.8 Approved and Non-Approved Concomitant Treatment**

Patients can receive full supportive care while on this study.

[REDACTED]

[REDACTED]

[REDACTED]

[REDACTED]

[REDACTED]

[REDACTED]

Live, attenuated vaccines (e.g., FluMist®) are prohibited within 4 weeks prior to initiation of study treatment, during treatment, and for 5 months after the final dose of atezolizumab and/or LOAd703.

Adenovirus-based vaccines (e.g., Vaxzevria, known as COVID-19 vaccine Astra Zeneca, J&J Covid-19 vaccine) are prohibited 3 months prior to initiation of study treatment, during treatment and 6 months after the final dose of LOAd703.

Need for palliative surgery as well as palliative local radiotherapy, e.g., for brain or bone metastasis, during the trial is accepted unless this prohibits tumor evaluation according to the RECIST-criteria.

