### 7.5.1 Tumor Size

Tumor size will be determined using a suitable imaging technique, depending on the localization of the tumor. Computer tomography (CT) will preferably be selected. Radiology exams will be performed every 9th week ( $\pm 1$  week) post-treatment initiation (i.e., [REDACTED] [REDACTED]). However, at screening, if the patient has been subjected to radiology examination within 3 weeks prior to registration, this imaging can be used as baseline at the discretion of the Investigator. Definitions of measurable disease and response to treatment will follow RECIST 1.1 criteria. For research purposes, other methods such as immune-related (ir) RECIST may be compared to the RECIST v1.1 outcome. Further, a study-specific tumor evaluation will also be performed (see *“Instructions for lesion selection and effect evaluation”* provided by the Sponsor in the Investigator Site File).

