### 7.6.5.2 *Handling of Dropouts or Missing Data*

For the purpose of calculating time since initial melanoma diagnosis, partial diagnosis dates will be imputed as follows:

- Missing day only will be imputed with the 1st of the month;
- Missing day and month will be imputed with 1st January.

No imputation will be done if the diagnosis date is completely missing.

If the imputed date is after the date of informed consent, the date of informed consent will be used instead (i.e., a time since diagnosis will be computed as 1 day).

The analysis of TTP and PFS will censor subjects without events at the date of the last evaluable tumor assessment. If a subject does not have any evaluable post-dose tumor assessments, they will be censored at the date of first dose plus 1 day. The analysis of OS will censor subjects without events at the date of last contact.

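### Best overall response has no stated end at RECIST v1.1 progression, so one patient can be an ORR responder and an earlier PFS event from the same scans

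*SAP*

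**What the plan says.** SAP 6.4.2.2 gives one secondary efficacy endpoint: "ORR defined as the proportion of subjects with a best overall response (BOR) of CR or PR (according to RECIST v1.1"). The next statement is that "BOR is defined as the best response achieved by a subject over the whole study". SAP 6.4.2.3 builds CBR on the same BOR.

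For the time-to-event endpoints, SAP 6.4.2.3 has "Progression free survival defined as the time from first dose of study treatment until progression according to RECIST v1.1 or death", and TTP uses the same progression. Neither definition asks for confirmation. On censoring, SAP 7.6.5.2 says "The analysis of TTP and PFS will censor subjects without events at the date of the last evaluable tumor assessment".

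The protocol makes scans after a first progression likely:

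- Under Progressive Disease in section 8.1, it warns that immune-driven swelling may be taken for progression. Progression that leads to stopping treatment "needs to be confirmed by radiological imaging at a later time point (within 4-12 weeks"), or by biopsy or serum marker. SAP 6.4.2 repeats this.
- Protocol 4.4.1 keeps off-treatment patients, including those with confirmed progression, in scheduled radiology.
- Protocol 5.8 says: "Need for palliative surgery as well as palliative local radiotherapy, e.g., for brain or bone metastasis, during the trial is accepted". The condition is that RECIST evaluation must remain possible.

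Protocol 7.5.1 treats immune-related criteria as a separate research comparison: "other methods such as immune-related (ir) RECIST may be compared to the RECIST v1.1 outcome".

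**The concern.** ORR and PFS come from the same scans and carry the same RECIST v1.1 label, but their observation windows differ. PFS and TTP stop at the first progression. BOR, read literally, does not stop. A programmer following SAP 6.4.2.2 would include every later scan.

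This matters because the plan itself expects tumours to swell and then shrink. Crediting a response seen only after progression is close in spirit to the immune-related reading that Protocol 7.5.1 sets apart for research. If such responses enter the row labelled RECIST v1.1, a reader of the report cannot tell how many of the responders had already progressed. The trial has a single arm, so no control group shares the effect, and ORR is the only secondary efficacy variable.

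**Working it through.** **No figure to reproduce.** The efficacy sample-size sections (Protocol 10.2.2, SAP 7.8.2) show no text, so no target ORR, alpha or power is visible. The check is a trace of the definitions, followed by an illustration of size.

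**Inputs**

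- BOR window: the whole study, with no visible stop (SAP 6.4.2.2).
- PR: a fall of at least 30% from baseline. PD: a rise of at least 20% from the smallest size, or a new lesion (Protocol 8.1).
- Scans: every 9 weeks, ±1 week (Protocol 7.5.1).
- Imaging confirmation of PD: 4 to 12 weeks later (Protocol 8.1).
- Efficacy sample: at least 25 response-evaluable patients at the MTD (Protocol Synopsis).

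**Step 1: trace one patient.** Set the baseline sum of diameters to 100. At week 9 a sum of 100 × 1.20 = 120 is PD. At week 18 a sum of 100 × 0.70 = 70 is PR. The gap is 18 − 9 = 9 weeks, or 7 to 11 weeks with ±1 week at each scan. It lies inside the 4-to-12-week confirmation interval, so the next routine scan can be the confirmation scan.

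| Endpoint | Result for this patient |
|---|---|
| ORR | Responder (BOR = PR at week 18) |
| CBR | Counted |
| TTP, PFS | Event at week 9 |

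If the week-18 sum is 100 instead and there is no new lesion, the scan is SD. BOR is then SD, the patient counts in CBR, and the PFS event at week 9 is unchanged.

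The reverse order does no harm. A patient with PR and then PD has BOR = PR under either window. Only patients whose first response (or, for CBR, first stable disease) comes after PD are affected.

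**Step 2: size per patient.** At n = 25 each affected responder contributes 1/25 = 4.0 percentage points. The counts below are illustrative. The intervals are exact (Clopper-Pearson) 95% intervals, which is an assumption because the ORR interval method is not visible.

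| BOR window | Responders | ORR (95% CI) |
|---|---|---|
| Whole study | 6/25 | 24% (9.4 to 45.1) |
| To first PD, one patient affected | 5/25 | 20% (6.8 to 40.7) |
| To first PD, two patients affected | 4/25 | 16% (4.5 to 36.1) |

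**Step 3: chance that it arises.** The documents give no frequency. With an assumed true share q of such patients, P(at least one in 25) = 1 − (1 − q)^25.

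| q (assumed) | Expected number, 25q | P(at least one) |
|---|---|---|
| 2% | 0.5 | 40% |
| 4% | 1.0 | 64% |
| 8% | 2.0 | 88% |
| 10% | 2.5 | 93% |

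**Step 4: local therapy.** Protocol 5.8 limits when palliative surgery or radiotherapy is accepted. It does not say which scans count in BOR afterwards, and the visible SAP text gives no rule for this in BOR or in censoring. This is a missing rule and is separate from the mismatch in Step 1, because local therapy is not a PFS event.

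**The case against.** **It is an estimand choice.** Best response and time to first progression measure different things, and a patient may appear in both without any arithmetic error. The plan foresees swelling, so a sponsor might want to credit later shrinkage. This stands as far as it goes. But the SAP does not state that choice, and the row is labelled RECIST v1.1 while immune-related criteria are kept separate. A deliberate choice should be written down and the affected patients shown.

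**The RECIST v1.1 label may import a cut-off.** The SAP cites the guideline without reproducing its BOR rules, so the documents cannot settle this. The explicit sentence that follows the label points to the entire study.

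**Confirmation may apply to PFS.** If only confirmed progression were an event, a patient whose swelling resolves would not be an event at week 9. The confirmation text concerns progression that leads to stopping treatment, and the TTP and PFS definitions do not refer to it. Scans also continue off treatment after confirmed progression, so the mismatch would shrink but not vanish.

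**Blacked-out text may hold the rule.** Parts of SAP 6.4.2.3, 7.6.3 and 7.6.4 and the text after the protocol's ORR definition are not readable. This is a real limit. Still, the BOR definition is readable and unqualified, and SAP 7.6.5.2, which deals with censoring, adds nothing on the point. If a rule exists, SAP 6.4.2.2 should refer to it.

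**ORR carries little formal weight.** Safety is the primary endpoint, there is no primary efficacy endpoint (SAP 6.4.2.1), and all results are descriptive (SAP 7.6.5.1). This stands and lowers the severity.

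**Conclusion.** The mismatch holds on the visible text: BOR has no stated end at progression, while TTP and PFS stop there. The effect is 4 points of ORR per affected patient at n = 25, and proportionately less if more patients are evaluable. It can only raise ORR and CBR or leave them unchanged. Whether it will matter in the data is unknown. The 40% to 93% range rests wholly on the assumed 2% to 10% share. Severity is moderate.

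A reader might infer more than this, and the documents do not support it:

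- *Responses to later systemic treatment also count.* Protocol 4.4.2 and 6.4 move patients who start another treatment to survival follow-up only, with the final clinical visit placed close to that start. This largely closes the window.
- *Any patient given local therapy is both a PFS event and a responder.* That is so only if progression came first. Protocol 5.8 also requires that RECIST evaluation stay possible, which narrows the gap.
- *A single unconfirmed scan is enough for PR or CR.* No visible text requires confirmation, but such a rule could sit in the blacked-out text, so this cannot be shown. The documents also give no measurement-error figure from which to size chance responses.

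**What to change.** In SAP 6.4.2.2, before database lock:

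1. State that the RECIST v1.1 BOR, and the ORR and CBR built on it, use assessments up to and including the first RECIST v1.1 progression. Use the same progression date as for TTP and PFS.
2. State in the same derivation that a response first seen after surgery or radiotherapy to a target lesion is not credited.
3. Report responses first seen after progression in a separate, labelled row, so that the information on delayed response is kept.
4. State which window applies to the additional BOR that includes mixed response, since that derivation reclassifies some progression visits.

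If an equivalent rule already stands in text that is not public, a cross-reference from SAP 6.4.2.2 is enough.

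The cost is SAP wording and one table row, with no extra scans and no change to patient care. The downside is that ORR and CBR may come out slightly lower.
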